### 3.8. Analysis Visit Windows

#### 3.8.1. Definition of Study Day

Study day will be calculated from the first dosing date of study drug and derived as follows:

- For postdose study days: Assessment Date – First Dosing Date + 1
- For days prior to the first dose: Assessment Date – First Dosing Date

Therefore, study day 1 is the day of first dose of study drug administration.

**Last Dose Date** is defined as the maximum, nonmissing, nonzero dose end date of treatment recorded on the Study Drug Administration eCRF form with “Study Drug Permanently Withdrawn” box checked for participants who prematurely discontinued or completed study drug according to the Study Drug Completion eCRF. Refer to [Appendix 2](#) for missing date imputation, if necessary.

**Last Study Date** is the latest of the study drug start dates and end dates, the in-person or phone visit dates, the vital sign or respiratory status collection dates, Flu-PRO Plus questionnaire collection date and the laboratory collection dates, including the 28-day follow-up visit date, and the death date (if applicable, only for participants who prematurely discontinued study according to the Study Completion eCRF).

**Baseline value** is defined as the last value obtained on or prior to the first dose date (and time, if available) unless otherwise specified (see Section [3.8.3](#)).

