### **8.5. Efficacy Analysis**

#### **8.5.1. Primary Analysis**

The primary endpoint of the study is the composite endpoint of COVID-19 related hospitalization or all-cause death by Day 28. The null hypothesis being tested is whether the ratio of proportion of COVID-19 related hospitalization or all-cause death is the same for the 2 treatment groups (ie, whether ratio is equal to 1 across all strata).

The hazard ratio, p-value, and 95% CI for the hazard ratio will be calculated using a Cox model with stratification factors as covariates.

Participants with missing outcomes for the primary endpoint due to prematurely discontinuation of the study will be censored at the date of last contact.

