### **3.6. Missing Data and Outliers**

#### **3.6.1. Missing Data**

In general, missing data will not be imputed unless methods for handling missing data are specified. Exceptions are presented in this document.

Participants with missing outcomes for the primary endpoint due to premature discontinuation of the study will be censored at last study date.

In this study, a missing pre-treatment laboratory result would be treated as normal (ie, no toxicity grade) for the laboratory abnormality summary. The handling of missing or incomplete dates for AE onset is described in Section 7.1.6.2, and for prior and concomitant medications in Section 7.4.

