#### 6.1.3. Primary Analysis of the Primary Efficacy Endpoint

The hazard ratio of COVID-19 related hospitalization or all-cause death between the two treatment groups will be estimated using a Cox model with stratification factors as covariates.

If a participant prematurely discontinues from the study prior to Day 28 or the hospitalization status is missing, the participant is censored at last study date or day 28 whichever is earlier. If a participant has a COVID-19 related hospitalization first and then dies, then date of the COVID-19 related hospitalization and status will be used for the primary analysis for this participant. If a participant has a non COVID-19 related hospitalization first and then dies without experiencing a COVID-19 related hospitalization, then date of the death and status will be used for the primary analysis for this participant.

The hazard ratio, p-value, 95% CI for the hazard ratio from Cox model, and proportion of COVID-19 related hospitalization or all-cause death at Day 28 from Kaplan-Meier estimate will be provided.

The FAS will be the primary analysis set for efficacy endpoint evaluation. The primary endpoint may be analyzed for each of the subgroups defined in Section 3.3.

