#### **Events with Completely Missing Onset Date**

An AE with a completely missing onset date is defined as TEAE if end date meets any of the 3 criteria specified above.

- 10) The precision in reporting numerical values should be as follows:

Raw measurements will be reported the same as the data captured electronically or on the eCRF for all but hematology and chemistry values.

Standard deviation and standard error will be reported to one more significant decimal place than the raw measurement.

Mean, median, minimum, Q1, Q3, and maximum will be reported to the same number of decimal places of the raw measurements.

Exceptions may be considered; for example, if more than 4 significant digits are provided for the measurement.

Precision for derived parameters as follows:

Parameters	Decimal Places
log 10 of SARS-CoV-2 viral load	2
Time-weighted average change in SARS-CoV-2 viral load	2
BMI	2
CCI	

- 11) Last dose date is not expected to be missing. However, if last dose date is missing, it will be imputed using the maximum of non-missing, non-zero dose, study drug start and stop dates.
- 12) Incomplete death dates will be imputed as the maximum of the study drug start dates, study drug end dates, clinic or phone visit dates (lvis28dt), laboratory visit dates (llab28dt), including the 28-day follow-up visit date plus 1.
- 13) Censoring rules

Time to hospitalization/death: If a participant prematurely discontinues from the study prior to Day 28 or the hospitalization status is missing, the participant is censored at last study date or day 28 whichever is earlier.

Time to negative SARS-CoV-2 viral load, participants are censored at the last assessment day and participants are required to have at least one postbaseline assessment.

Time to alleviation of baseline COVID-19 symptoms:

- For overall baseline symptom alleviation, participants are censored at the last assessment day that at least one of the baseline symptoms was assessed. For baseline symptom alleviation for each domain, participants are censored at the last assessment day that at least one of the baseline symptoms within that domain was assessed

- 14) Graded Laboratory Abnormalities Summary

The following labels will be used for laboratory abnormalities and Grade 3 or 4 laboratory abnormalities summary tables and listings:

Battery	Lab Test Label Used in I-labtox Listing	Toxicity Direction	Lab Test Label Used in t-labtox Table
Hematology	Hemoglobin	Decrease	Hemoglobin (Decreased)

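### The primary censoring rule can carry a participant whose hospitalization status is unknown to Day 28 as event-free; the effect is very small and a wording change removes it

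*SAP*

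**What the plan says.** The trigger in SAP 6.1.3 is: "If a participant prematurely discontinues from the study prior to Day 28 or the hospitalization status is missing". The consequence is that "the participant is censored at last study date or day 28 whichever is earlier". SAP Appendix 2, item 13, repeats the rule for the programmers.

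SAP 3.8.1 defines Last Study Date. It "is the latest of the study drug start dates and end dates, the in-person or phone visit dates", followed by vital-sign or respiratory dates, the "Flu-PRO Plus questionnaire collection date and the laboratory collection dates", "including the 28-day follow-up visit date, and the death date". The death date enters only for participants recorded as having left the study prematurely.

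Protocol 8.5.1 says that participants with a missing primary outcome after premature discontinuation "will be censored at the date of last contact".

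SAP 6.1.4 gives one alternative analysis for missing outcomes, an optional stratified CMH test. It counts a missing outcome as no hospitalization or death.

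**The concern.** A censoring date for time to hospitalization or death should be the last day on which the participant was known to be free of both. Last Study Date answers a different question: when was anything on the list last recorded?

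The two can differ in two ways that reach Day 28:

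- **(a) Missing status.** The SAP foresees participants whose hospitalization status is missing. If such a participant has any listed date at or after Day 28, the censoring day is Day 28. For the Cox model and the Kaplan-Meier estimate this is the same as completing follow-up without an event.
- **(b) Late death.** A participant leaves early and later dies after Day 28. The death becomes Last Study Date, and the minimum with Day 28 carries the participant to Day 28 although nobody knew the hospitalization status in between. A death date is not naturally a contact, so protocol 8.5.1 does not cover this use, and SAP 2.3 and 6.4 do not list it as a change.

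Unobserved time then stays in the risk set, which lowers the event proportions slightly. If such cases differ by arm, the hazard ratio moves too. The CMH analysis cannot reveal this, because it also treats missing as no event.

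**Working it through.** **1. The plan's own figure.** Inputs from protocol 8.9: 12% and 6.6% event rates, overall rate 9.3%, N = 1264, 5% dropout, two-sided 0.05.

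- Hazard ratio = ln(1 − 0.066) / ln(1 − 0.12) = 0.534, as stated.
- Events = 1264 × 0.95 × 0.093 = 111.7.
- Power, with R² = 0 and σ² = 0.25: √111.7 / 2 × |ln 0.534| − 1.96 = 1.35, which gives 91.2%. The stated figure of more than 90% reproduces.

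**2. The rule applied to test cases.** Hospitalization review (medically attended visit information) is scheduled on Days 1, 2, 3, 7, 14 and 28 (protocol Appendix 2).

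| Case | Last Study Date | Result under the SAP | Last known status |
|---|---|---|---|
| Reviewed Day 7, withdrew, died Day 31 | 31 | censored Day 28 | Day 7 |
| Visit on Day 28, status missing there | 28 | censored Day 28 | Day 14 |
| Visit on Day 25, status missing there | 25 | censored Day 25 | Day 14 |
| Reviewed Day 7, diary to Day 14, then lost | 14 | censored Day 14 | Day 7 |
| Reviewed Day 7, withdrew, died Day 20 | 20 | event Day 20 (intended) | Day 7 |

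The first two rows are cases (b) and (a). The last row needs care. Read literally, the censoring sentence in 6.1.3 has no condition that the participant is event-free, so it could censor this death. SAP 6.1.1 and the rest of 6.1.3 show that an event is meant. The CMH wording asks only whether an event came before discontinuation, so it could also miss this death.

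**3. Size by hand.** Expected events at 584 randomized (SAP 2.1.1): 584 × 0.093 = 54.3, or 51.6 after removing 5% dropout.

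- Dropouts: 584 × 0.05 = 29.2. If loss times are uniform over 28 days, on average half the window is unobserved. If every dropout were carried to Day 28, the uncounted events would be 29.2 × 0.093 × 0.5 = 1.36. If half were carried, 0.68. One whole event would need 1 / 1.36 = 74% of dropouts to be carried.
- Missing status with last known status at Day 14: 0.093 × 14/28 = 0.047 events each, so about 21 such participants make one event. The documents give no count.
- With 292 per arm (584 / 2), each carried participant enlarges that arm's risk set by about 1/292 = 0.3%.

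**4. Size by integration.** Let λ be the constant hazard giving 12% or 6.6% by Day 28, S(t) = exp(−λt), d the fraction lost at a uniform time, and s the share of those carried to Day 28.

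- Event density = λS(t)[(1 − d) + d(1 − t/28)].
- Risk set = (1 − d)S(t) + ds[(1 − t/28)S(t) + (1/28)∫₀ᵗS(u)du] + d(1 − s)(1 − t/28)S(t).
- Kaplan-Meier proportion = 1 − exp(−∫ density / risk set).

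| Lost, placebo / RDV | Share carried | KM placebo | KM RDV | HR | Events in 584 |
|---|---|---|---|---|---|
| any | 0 | 12.0% | 6.6% | 0.534 | 54.3 |
| 5% / 5% | half | 11.9% | 6.5% | 0.534 | 53.6 |
| 5% / 5% | all | 11.7% | 6.4% | 0.534 | 53.0 |
| 5% / 2% | all | 11.7% | 6.5% | 0.543 | 53.3 |
| 2% / 5% | all | 11.9% | 6.4% | 0.526 | 53.5 |
| 10% / 2% | all | 11.4% | 6.5% | 0.558 | 52.4 |
| 2% / 10% | all | 11.9% | 6.3% | 0.512 | 53.0 |

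The fully carried, balanced case loses 54.3 − 53.0 = 1.3 events, in line with step 3. Loss by arm, uniform loss times and constant hazards are assumptions; the documents give only the overall 5%.

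**The case against.** The case against is strong on size and scope.

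- **Any contact counts.** A reader might infer this. The SAP list is closed, and its scheduled dosing, laboratory and vital-sign dates fall on days that also have a hospitalization review. Only the FLU-PRO Plus diary regularly adds dates between reviews, and it stops at Day 14.
- **Admissions are unseen between reviews.** Not so. In-patient hospitalization is a serious adverse event (protocol 7.1.2), to be recorded within 24 hours throughout the study (7.3.3), and the endpoint uses what the site reports (SAP 6.1.1). Cutting follow-up back to the last scheduled review, while still accepting admissions reported in between, would bias the event proportions upward. The diary dates therefore do not need to leave the main rule.
- **The death date hides deaths.** It does not. A death by Day 28 is itself an event. Only later deaths in premature discontinuers matter, and required reporting after the follow-up visit ends 30 days after the last dose, about Day 33 for a last dose on Day 3.
- **The SAP contradicts itself or the protocol.** SAP 3.6.1 begins "In general, missing data will not be imputed", but allows for specified methods, and 6.1.3 is one. A visit, laboratory or diary date is a reasonable reading of last contact. Only the death date goes beyond it.
- **The hazard ratio is materially biased.** The shifts above need loss that differs by arm and near-complete carrying to Day 28. The documents give no sign of either, and the trial is double-blind.

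What stands is narrow: cases (a) and (b) follow from the stated rule, and no planned analysis would show their effect.

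**Conclusion.** The concern holds as a minor defect in one derived date. The rule can score unknown hospitalization status as event-free through Day 28 in cases (a) and (b). The expected effect at 584 randomized is probably under one event out of about 54. The 1.3-event figure is a ceiling among dropouts, because it needs all of them to have a listed date at or after Day 28. With balanced loss the hazard ratio is unchanged to three decimals.

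This rests on the planned 5% dropout, constant hazards and non-informative loss. The number of participants with missing status is not given. Informative loss, such as admission elsewhere followed by loss of contact, could matter more and was not modelled. A better censoring date would not recover such an admission; it would only stop crediting the unobserved days.

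**What to change.** In SAP 6.1.3 and Appendix 2, item 13, for the primary endpoint:

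1. Do not let a death after Day 28 enter the censoring date.
2. Censor a participant with missing hospitalization status at the last date on or before Day 28 on which status was known, whether from an in-person or phone review or from other site reporting.
3. State that a death by Day 28 is an event even after discontinuation, and align the CMH wording in 6.1.4.
4. Keep FLU-PRO Plus dates in the main rule, and exclude them in a sensitivity analysis.

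The cost is one derived date from data already collected, a few lost follow-up days, and a note that this refines the last-contact rule of protocol 8.5.1. If the SAP is already final, its introduction allows the change to be documented in the clinical study report.

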#### 3.8.2. Analysis Visit Windows

Participant visits might not occur on protocol-specified days. Therefore, for the purpose of analysis, observations will be assigned to analysis windows.

The analysis windows for Vital signs are provided in [Table 3-1](#).

**Table 3-1. Analysis Visit Windows for Vital signs**

Nominal Visit	Nominal Study Day	Visit Window Study Day	
		Lower Limit	Upper Limit
Baseline	1	(none)	1 (Pre Dose)*
Day 1	1	1 (Post Dose) *	1 (Post Dose)
Day 2#	2	2	2
Day 3#	3	3	4
Day 7	7	5	9
Day 14	14	10	21
Day 28	28	22	(none)

\* For baseline, the upper limit includes values collected at or prior to the first dose date/time. For Day 1, the lower limit includes values collected after the first dose date/time on Day 1.

# The pre dose and post dose timepoints for Days 2 and 3 will be based on nominal time point. The analysis windows for Weight, and Respiratory status are provided in [Table 3-2](#).

**Table 3-2. Analysis Visit Windows for Weight, SpO2 and Respiratory status**

Nominal Visit	Nominal Study Day	Visit Window Study Day	
		Lower Limit	Upper Limit
Baseline	1	(none)	1 (Pre Dose)*
Day 2	2	1 (Post Dose) *	2
Day 3	3	3	4
Day 7	7	5	9
Day 14	14	10	21
Day 28	28	22	(none)

\* For baseline, the upper limit includes values collected at or prior to the first dose date/time. For Day 2, the lower limit includes values collected after the first dose date/time on Day 1.

The analysis windows for PCR are provided in [Table 3-3](#).

**Table 3-3. Analysis Visit Windows for PCR**

Nominal Visit	Nominal Study Day	Visit Window Study Day	
		Lower Limit	Upper Limit
Baseline	1	(none)	1 (Pre Dose)
Day 2	2	1 (Post Dose)	2
Day 3	3	3	4
Day 7	7	5	9
Day 14	14	10	21
Post Day 14	22	22	none

The analysis windows for Chemistry and Hematology laboratory parameters are provided in [Table 3-4](#).

**Table 3-4. Analysis Visit Windows for Hematology, Coagulation and Chemistry Laboratory Tests**

Nominal Visit	Nominal Study Day	Visit Window Study Day	
		Lower Limit	Upper Limit
Baseline	1	(none)	1 (Pre Dose)
Day 3	3	1 (Post Dose)	4
Day 7	7	5	9
Day 14	14	10	(none)

FLU-PRO Plus Questionnaire were to be collected daily from Day 1 through Day 14; therefore, windows are not assigned and results will be summarized for each Study Day.

### **3.8.3. Selection of Data in the Event of Multiple Records in an Analysis Visit Window**

Depending on the statistical analysis method, single values may be required for each analysis window. For example, change from baseline by visit usually requires a single value, whereas a time-to-event analysis would use all data regardless of analysis window.

If multiple valid, nonmissing measurements exist in an analysis window, records will be chosen based on the following rules if a single value is needed:

- For baseline, the last nonmissing value on or prior to the first dosing date (and time, if available) of study drug will be selected, unless specified differently. If there are multiple records with the same time or no time recorded on the same day, the baseline value will be the average of the measurements for continuous data, or the measurement with the lowest severity for categorical data.
  - For baseline, if both local lab and central lab results are available, central lab results will be selected first for baseline, local lab results will be used when central lab results are missing.
  - For FLU-PRO Plus data, if there are multiple records on Day 1, the baseline value will be selected as follows:
    - The record closest to the dosing day will be selected.
    - If there are more than 1 records on the selected day with different times, the least severe score will be selected as baseline. If there are multiple records with same severity, the measurement with the lowest severity at later time will be selected.

- For postbaseline values (other than PCR negative confirmation and PCR for time-weighted average change from baseline (DAVG)):
  - The record closest to the nominal day for that visit will be selected.
  - If there are 2 records that are equidistant from the nominal day, the later record will be selected.
  - If there is more than 1 record on the selected day, values will be selected for analysis as follows:
    - For PCR, if there is more than 1 record on the selected day, the latest value will be selected. If there are multiple records with the same time or no time recorded on the same day, the geometric mean value (copies/mL) will be taken. For laboratory values (other than PCR) and SpO2, if there is more than 1 record on the selected day, the average value will be selected.
    - For FLU-PRO Plus data, if there are more than 1 record on the same day, the worst value will be selected.
    - For RBC Morphology result, if there is more than 1 record on the selected day, all results will be selected.
    - For vital signs, the pre dose and post dose timepoints for Days 2 and 3 will be summarized by nominal time point. If there is more than 1 record on a time point, the average will be taken.
    - For other parameters, if there is more than 1 record on the selected day, the average will be taken for continuous data and the worst severity will be taken for categorical data, unless otherwise specified.
- For postbaseline values of PCR negative confirmation:
  - All available data will be used to derive negative confirmation except if there are multiple records on the same day, the worst value will be used for negative confirmation for that day
  - The record closest to the nominal day for that visit will be selected.
  - If there are 2 records that are equidistant from the nominal day, the later record will be selected.
- For postbaseline values PCR for DAVG calculation:
  - All values from different days within an analysis windows will be used for DAVG calculation.

- If there is more than 1 record on a study day, the latest value will be selected. If there are multiple records with the same time or no time recorded on the same day, the geometric mean value (copies/mL) will be taken.

## 4. SUBJECT DISPOSITION

### 4.1. Subject Enrollment and Disposition

The number and percentage of participants randomized at each investigator site will be summarized by treatment group and overall using the Safety Analysis Set and All Randomized Analysis Set. The number and percentage of participants enrolled by randomized stratum will be summarized using stratum assignment captured in the IXRS. Discrepancy between IXRS and clinical database will be noted if applicable. The denominator for this calculation will be the number of participants in the Safety Analysis Set.

The summary of subject disposition will be provided by treatment group and overall for all screened participants. This summary will include the number of participants screened, screen failure participants who were not randomized, participants who met all eligibility criteria and were not randomized, participants randomized, participants randomized but never treated, participants in the Safety Analysis Set, participants in the modified FAS and participants in the FAS.

In addition, the number and percentage of the participants in the following categories will be summarized:

- Completed randomized treatment on study drug as recorded on the Study Drug Completion form
- Prematurely discontinuing study drug prior to completion with summary of reasons for discontinuing study drug as recorded on the Study Drug Completion form
- Completed study
- Prematurely discontinuing from study (with summary of reasons for discontinuing study) as recorded on the Study Completion form

The denominator for the percentages of participants in each category will be the number of participants in the Safety Analysis Set.

No inferential statistics will be generated. A data listing of reasons for premature study drug/study discontinuation will be provided.

### 4.2. Extent of Study Drug Exposure and Adherence

Number of doses received will be summarized by treatment group for the Safety Analysis Set.

### 4.3. Protocol Deviations

A listing will be provided for all randomized participants who violated at least 1 inclusion or exclusion criterion. The listing will include the criteria not met.

Protocol deviations occurring after participants entered the study are documented during routine monitoring. The number and percentage of participants with important protocol deviations and the total number of important protocol deviations by deviation reason (e.g., nonadherence to study drug, violation of select inclusion/exclusion criteria) will be summarized by treatment group for the FAS. A by-subject listing will be provided for those participants with important protocol deviation.

